Cases of Diparetic and Quadiparetic spastic CP between 4-14 years old selected among the patients referred to the pediatric neurology outpatient department of Children's Medical Center Hospital (CMC) affiliated to Tehran University of Medical Sciences. Due to necessity of HLA matching of hematopoietic stem cells derived from allogeneic umbilical cord (MNC) group we selected 150 cases of referred patients with our inclusion criteria and HLA analysis were done for these patients and then 36 cases of class 6 matched patients enrolled to the MNC group and 72 cases among the remaining patients randomly divided to mesenchymal stem cells derived from allogeneic umbilical cord (MSC) and control group . Therefore 108 cases enrolled in 3 divided groups of 36 patients.

Baseline clinical and neuroimaging evaluations were done for all of the 108 cases. Patients admitted in CMC and five million cell /kg of MNC and one million cell / kg of MHC stem cells that prepared in Royan Stem Cell Technology Co and Cell Tech Pharmed Co respectively were injected intrathecally with sedation. Only one dose of intrathecal injection was done for each participant .In the control group after insertion of the needle into the skin with an appearance of simulation of lumbar puncture no injection were done without the awareness of the patients or their parents. All of the participants admitted for observation and management of early side effects and discharged after 24 hours. Acute side effects and probable long term side effects will be reported and noted on our preformed questioners . Both participants and clinical evaluators are not aware of the 3 divided groups and our study is double blind.

Follow up clinical evaluators will be done at 1, 3, 6, and 12 months after injection for all of the participants .The intervention and control groups referred for neurorehabilitation with an identical protocol , that will be continued during the 12 months of follow up .

Standard brain Magnetic Resonance Imaging (MRI) with Magnetic Resonance Spectroscopy (MRS) and Diffusion Tensor Imaging (DTI) were done before injection and will be repeated after 12 months of clinical follow up.

For ethical consideration, we promised in the consent form that stem cell therapy will be done free of charge for participants of control group after 12 months of evaluation.

Inclusion criteria:

- Spastic cerebral palsy (Diparetic , Quadriparetic)
- Ages between 4 - 14 years

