- Gross motor function classification (GMFC) between 2 -5
- No seizure disorder or with controlled seizures

- Evidence of definite acquired abnormal imaging findings compatible with Cerebral Palsy
- Informed consent is taken from their parents

Exclusion criteria:

- Normal brain MRI
- Progressive neurologic diseases
- Cortical malformations
- TORCH (Toxoplasmosis, Other, Rubella, Cytomegalovirus and Herpes Infections)
- Other types of cerebral palsy including athetoid , atonic , ataxic , and mixed type
- Acute intercurrent infections such as Hepatitis C Virus (HCV), Hepatitis B Virus (HBV), Human Immunodeficiency Virus (HIV) Malignancies
- Hemorrhagic diathesis
- Severe anemia (Hemoglobin less than 8 g/dl)
- Ventilator dependent pulmonary diseases
- Renal insufficiency
- Severe liver dysfunction

Primary outcome measures:

Different scoring systems such as Gross Motor Functional Classification System (GMFCS) , Gross Motor Function Measure Score (GMFM66) , Manual Ability Classification System (MACS) , Pediatric Evaluation of Disability Inventory (PEDI) , CP Quality of Life (QOL) , Life Habits Questionnaire and Modified Ashworth scale for spasticity were done at baseline and then will be repeated in follow ups until 12 months of final evaluation.

Change and Improvement to baseline of motor function with GMFCS score
Change and Improvement to baseline of motor function with Gross Motor Function Measure Score (GMFM66)
Change and Improvement to baseline of Manual Ability Classification System (MACS)
Change and Improvement to baseline of Pediatric Evaluation of Disability Inventory (PEDI).
Improvement of CP QOL
Improvement of Life Habits Questionnaire
Change and Improvement to baseline of Spasticity of patients according to Ashworth scale.
Improvement of developmental status according to Stanford Binet scale.

Secondary Outcome Measures:

Change and Improvement to baseline of Brain imaging findings according to MRI, MRS and DTI (baseline and at 12 months after injection)

Ethic Committee Approval:

Tehran University of Medical Sciences - 2017-06-06

Ethics committee Reference number: IR.TUMS.VCRREC.1996.2506.

Iranian Registry of Clinical Trials (IRCT) :

Trial Id No 7342 Registration date 2017-07-12 - IRCT201706176907N13

Sample size calculation:

To determine the sample size and attainment the maximum power, Sample size was calculated, based on the standard deviation reported from the study of Zali A,

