et.al(($\sigma=10$) and Type I (α) error 0.05 and power 80% to achieve 12 score difference in mean of GMFC after intervention. The minimum number of patients required for this study was estimated 108 subjects, which are in each of the three groups MNC, MSC and Control 36 patient allocated, respectively.

Number of subjects N in each of two groups (Diggle *et al.*, 2002)

$$N = \frac{2(z_{\alpha} + z_{\beta})^2 (1 + (n - 1)\rho)}{n[(\mu_1 - \mu_2)/\sigma]^2}$$

- σ^2 is the assumed common variance in the two groups
- $\mu_1 - \mu_2$ is the difference in means of the two groups
- n is the number of timepoints
- ρ is the assumed correlation of the repeated measures

Randomization:

The patients are randomly allocated into three groups of intervention and control using a balanced block randomization technique. To do that, they were divided into blocks of 6 and 9. All subjects randomly allocated with online randomization software to generate random-number sequences. {Sealed Envelope Ltd. 2015.

Create a blocked randomization list. [Online] Available from:

<https://www.sealedenvelope.com/simple-randomiser/v1/lists> [Accessed 15 Dec 2015]}. Coordinator and Physician responsible for assessing inclusion / exclusion criteria and registering individuals are blind.

Due to necessity of HLA matching of hematopoietic stem cells derived from allogeneic umbilical cord (MNC) group we selected 150 cases of referred patients with our inclusion criteria and HLA analysis were done for these patients and then

36 cases of class 6 matched patients enrolled to the MNC group and 72 cases among the remaining patients randomly divided to mesenchymal stem cells derived from allogeneic umbilical cord (MSC) and control group . Therefore 108 cases enrolled in 3 divided groups of 36 patients.

Statistical analysis:

Intent-to-treat approach will be used to compare the mean GMFC as the initial outcome among the three groups. One-way analysis of variance will be used to investigate the difference between mean GMFC according to the study variables. Then, the post-hoc Scheffe test is used to determine the means differences. Moreover, backward stepwise multivariate linear regression will be used to evaluate the relationship between variables. The GEE model is used to evaluate the outcome changes over time. All analyses were performed at a significance level of 0.05 using the Stata 11 (StataCorp, College Station, TX, USA) statistical software.

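### The outcome section lists eight unranked primaries; the sizing and analysis use only mean GMFC, whose scale, visit and metric are undefined and whose deciding test is ambiguous

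*Combined protocol and SAP*

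**What the plan says.** All references are to the combined protocol and SAP.

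- **Primary outcome measures** lists eight items: GMFCS, GMFM-66, MACS, PEDI, CP QOL, Life Habits, Ashworth and Stanford Binet. There is no ranking, co-primary rule or split of alpha. Five of the eight are worded as change from baseline, for example "Change and Improvement to baseline of motor function with Gross Motor Function Measure Score (GMFM66"; the other three speak only of improvement.
- **Statistical analysis** will "compare the mean GMFC as the initial outcome among the three groups" by one-way ANOVA, after which "the post-hoc Scheffe test is used to determine the means differences". It adds a backward stepwise regression and, separately, "The GEE model is used to evaluate the outcome changes over time". Every analysis is at 0.05.
- **Sample size calculation** assumes SD 10 and "power 80% to achieve 12 score difference in mean of GMFC after intervention". Its formula is for repeated measures and includes a term that "is the assumed correlation of the repeated measures", but gives no value for that term or for the number of timepoints.
- **Inclusion criteria** contain the only expansion of GMFC: "Gross motor function classification (GMFC) between 2 -5".
- **Study design** sets the visits: "Follow up clinical evaluators will be done at 1, 3, 6, and 12 months after injection". The outcome section calls 12 months the final evaluation but does not make it the primary visit.

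**The concern.** The outcome section and the analysis section do not describe the same primary objective, and the name that should link them is used in two incompatible ways. GMFC is a class from 2 to 5 at entry, yet it carries a 12-point difference with SD 10 in the sizing. One of those uses must refer to something else, and the document does not say what.

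Three further choices are open: which of four visits counts, whether the outcome is change from baseline or the follow-up score, and (less clearly) whether ANOVA or GEE decides. As written, nothing prevents these from being settled after the data are seen. A 5% error rate for the primary claim needs one measure, one visit, one metric and one test fixed in advance.

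**Working it through.** **1. The plan's own figure.** With two-sided 0.05 (sidedness is not stated), 80% power, 12 points and SD 10, the printed formula gives N = 2(1.960 + 0.842)² × (1 + (n − 1)ρ) / (n × 1.2²).
- n = 1: 15.70 / 1.44 = 10.9, so 11 per group.
- n = 4: 6.8 at ρ = 0.5 and 9.3 at ρ = 0.8.

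The stated 36 per group is not reproduced for any n with ρ up to 1. That is a separate issue. It matters here only because the sizing therefore does not reveal which visit or model was intended.

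**2. Can GMFC on levels 2 to 5 carry the planning figures?**
- Largest difference in means: 5 − 2 = 3, against 12 planned.
- Largest SD in 36 patients, with 18 at each end (mean 3.5, each 1.5 away): √(36 × 1.5² / 35) = 1.52, against 10 planned.
- Smallest spread that allows SD 10 in 36 patients: 20 × √(35/36) = 19.7 points.

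The planning figures cannot refer to values from 2 to 5. The document gives that range for entry only and states no limits for follow-up scores.

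**3. What the open choices could cost.** These are simulations with no true effect: three groups of 36, normal data, exchangeable groups and a common correlation r. The pooled df are 105, the F critical value is 3.083 and the Scheffé critical value is √(2 × 3.083) = 2.483. The document gives no correlations, so every r is an assumption.

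All eight primary, any one claimable:

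| r between outcomes | 0 | 0.3 | 0.5 | 0.8 |
|---|---|---|---|---|
| Any ANOVA significant | 34% | 30% | 26% | 16% |
| Any Scheffé pair significant | 27% | 24% | 21% | 13% |

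Check at r = 0: 1 − 0.95⁸ = 33.7%.

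One outcome, ANOVA at any of the four visits may count:

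| r between visits | 0.3 | 0.5 | 0.8 | 0.9 |
|---|---|---|---|---|
| Any visit significant | 17.5% | 16% | 12% | 10% |

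One outcome, either the 12-month ANOVA or a second longitudinal test may decide:
- Second test is a group comparison of each patient's four-visit average: about 8.5%, 8%, 7% and 6% at the same four values of r.
- Second test is a group comparison of each patient's slope over months 1, 3, 6 and 12: about 9% to 10% at every r.

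Both stand in for a GEE effect that the plan does not specify. A slope is closer to its wording about change over time. The 12-month ANOVA alone stays at 5%.

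**4. Power if several primaries are kept.** For a Scheffé pair at 12 points, SD 10 and 36 per group, the standard error is 10 × √(2/36) = 2.357 and the noncentrality is 12 / 2.357 = 5.09.
- At 0.05 (critical value 2.483): power 99.5%; 7.9 points detectable at 80% power.
- At 0.05/8 = 0.00625 (critical value 3.265): power 96.3%; 9.7 points detectable at 80% power.

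**The case against.** The strongest reply is that the analysis section already names one primary. Its term for the outcome most naturally means primary, the trial is sized on that outcome alone, and the ANOVA with Scheffé follows directly. GEE is given a different task, and 12 months is called the final evaluation. On that reading there is one outcome, one obvious visit and one test, in a phase II trial.

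Much of this stands. ANOVA against GEE is an ambiguity rather than a conflict: ANOVA is the ordinary reading, and only the repeated-measures formula points the other way. What the reply does not answer is that eight primaries remain listed, GMFC is not among them, its only definition is incompatible with the sizing, and the visit and metric are not designated. Scheffé adjusts for comparisons between groups, not for outcomes, visits or models.

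Three stronger readings are tempting, and the document does not support them:
- **That the plan has a false-positive rate of 34%.** Nothing says that success on any one of the eight suffices, and the analysis section favours a single primary.
- **That GMFC must mean GMFM-66.** It is a candidate, but the document gives no range for that measure and does not show which scale the cited SD came from.
- **That fixing visit and test secures 5%.** This assumes exchangeable groups, whereas the MNC group is chosen by HLA match and only the other 72 patients are randomised.

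**Conclusion.** The point holds. There is a real contradiction, not just missing detail: eight unranked primaries in one section, one sized and analysed outcome in another, and a name for that outcome whose only definition (levels 2 to 5) cannot carry 12 points with SD 10. The visit and the metric are undefined, and the deciding test is ambiguous.

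The scale contradiction rests on the document's own figures. The error rates do not. They are conditional on assumed correlations, normal data, exchangeable groups and a permissive rule for what counts: about 34% to 16% for any of eight outcomes, 17.5% to 10% for any of four visits, and 6% to 10% for either of two tests. They show what is left unprotected.

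This should be corrected, with medium confidence. The failure of 36 per group to reproduce and the non-random MNC allocation are separate issues.

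**What to change.** In a dated amendment before unblinding, with the ethics and registry entries updated to match:

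1. State which listed measure GMFC means in the sizing and analysis sections, with the sponsor confirming that 12 points and SD 10 refer to it. Use one name throughout.
2. Make that measure at 12 months the single primary outcome, and state whether it is change from baseline or the 12-month score.
3. Name one deciding test. Label the others, including the stepwise regression, as supportive, and make the sample-size basis match the deciding test.
4. Move the other seven outcomes to secondary. Alternatively, keep several primaries under Holm or a fixed sequence, with an expected effect and SD stated for each.

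Cost: no added patients for the sized outcome. The other seven scales can no longer each support an unadjusted primary claim. If all eight stay primary, even plain Bonferroni with the planned Scheffé comparisons lowers power for the sized outcome only from 99.5% to 96.3%, provided 12 points and SD 10 are right for it. Power for the other seven is unknown, because the document gives no effect or SD for them. The amendment does not resolve the sample-size discrepancy or the MNC allocation.

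### The three-group ANOVA of mean GMFC fixes no visit, no score form and no baseline covariate, although baseline was assessed in all 108 children

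*Combined protocol and SAP*

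**What the plan says.** The Statistical analysis section opens with "Intent-to-treat approach will be used to compare the mean GMFC as the initial outcome among the three groups". It continues with "One-way analysis of variance will be used to investigate the difference between mean GMFC according to the study variables", and next "Then, the post-hoc Scheffe test is used to determine the means differences". Two further methods follow: "backward stepwise multivariate linear regression will be used to evaluate the relationship between variables", and "The GEE model is used to evaluate the outcome changes over time". The section gives no visit, no model terms and no list of candidate variables.

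Other sections bear on what is analysed:

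- Primary outcome measures says the scales "were done at baseline and then will be repeated in follow ups until 12 months of final evaluation", and lists the motor outcomes as change from baseline.
- Sample size calculation gives "power 80% to achieve 12 score difference in mean of GMFC after intervention", with SD 10. Its formula is a repeated-measures one, in which "n is the number of timepoints" and a within-child correlation appears. Neither is given a value.
- Study design reports baseline clinical evaluation of all 108 children and follow-up at 1, 3, 6 and 12 months.
- Inclusion criteria uses GMFC for a classification level, 2 to 5 at entry.
- Randomization says all three groups were allocated by blocked randomisation. Study design, and a later paragraph of Randomization, say 36 HLA-matched children filled the MNC group and only the other 72 were randomised.

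**The concern.** An ANOVA of mean GMFC could be run on the 12-month value, on change to 12 months, or on any of three earlier visits, and each would be consistent with the text. These analyses can give different estimates and intervals from the same children. The choice should not be open once data are seen.

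Baseline motor score is an obvious candidate predictor of later motor score, and it has already been collected. A one-way ANOVA of follow-up values ignores it, and a change score uses it with a fixed coefficient of one. Backward selection may drop it. For the randomised MSC versus control contrast, what is at stake is precision, not bias. If the MNC group was filled by HLA match, its baseline scores need not resemble those of controls. The choice between change and adjustment then moves the estimate itself.

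**Working it through.** **The plan's own figure.** With two-sided alpha 0.05 (sidedness is not stated), power 80%, difference 12, SD 10 and one timepoint, the formula gives 2 × (1.960 + 0.842)² / 1.2² = 10.9, so 11 per group. More timepoints give no more than this. The stated 36 is not reproduced. That is a separate matter; here it means only that power is ample.

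**Unadjusted ANOVA.** Inputs: 36 per group and SD 10 (Sample size calculation), taking 10 as the SD of the score analysed. Error df = 108 − 3 = 105.

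- SE of a pairwise difference = 10 × √(2/36) = 2.357.
- Critical values: t = 1.983; Scheffe = √(2 × F(0.95; 2, 105)) = 2.483.
- 95% half-widths: 1.983 × 2.357 = 4.67 (t); 2.483 × 2.357 = 5.85 (Scheffe).
- Power for 12 points (noncentral t): 99.9% (t); 99.5% (Scheffe).
- Difference detectable with 80% power under Scheffe: 7.85.

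**Baseline-adjusted comparison.** Assumptions: linear score, equal variance σ² at baseline and 12 months, near-balanced baselines, and a baseline-to-12-month correlation r that the documents do not give.

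- Follow-up variance: σ².
- Change variance: 2(1 − r)σ².
- Adjusted variance: (1 − r²)σ².
- Adjusted/change = (1 + r)/2. Adjusted/follow-up = 1 − r².
- Cost: one error degree of freedom (104 left).

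The half-widths and detectable differences below are the unadjusted figures times the square root of the relevant ratio.

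| | r = 0.3 | r = 0.6 | r = 0.9 |
|---|---|---|---|
| Variance, adjusted/change | 0.65 | 0.80 | 0.95 |
| Variance, adjusted/follow-up | 0.91 | 0.64 | 0.19 |
| Half-width t (Scheffe), if 10 is the change SD | 3.8 (4.7) | 4.2 (5.2) | 4.6 (5.7) |
| Half-width t (Scheffe), if 10 is the follow-up SD | 4.5 (5.6) | 3.7 (4.7) | 2.0 (2.6) |
| Detectable, Scheffe, if 10 is the change SD | 6.3 | 7.0 | 7.7 |
| Detectable, Scheffe, if 10 is the follow-up SD | 7.5 | 6.3 | 3.4 |

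**When baselines differ.** With a gap of d SD between two groups, the adjusted variance is multiplied by about 1 + d²/(105 × 2/36) = 1 + d²/5.83. That is 1.04 at d = 0.5 and 1.17 at d = 1. At r = 0.9 the adjusted/change ratio of 0.95 becomes 0.95 × 1.06 = 1.01 at d = 0.6 and 0.95 × 1.17 = 1.11 at d = 1. The advantage over change has then gone. The estimates also separate: the adjusted contrast minus the change contrast is (1 − r) × gap, or 0.7, 0.4 and 0.1 points per point of gap at the three values of r.

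**Baseline-by-visit term in a GEE.** Take illustrative correlations of 0.9, 0.85, 0.75 and 0.6 at 1, 3, 6 and 12 months. One common slope at their average, 0.775, gives a 12-month variance of 1 − 2(0.775)(0.6) + 0.775² = 0.671, against 1 − 0.6² = 0.640. The SE rises by √(0.671/0.640) − 1, about 2.4%. It also leaves 0.6 − 0.775 = −0.175 points in the 12-month contrast per point of baseline gap.

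**Scale.** Entry levels of 2 to 5 span three steps, so a 12-point difference in means cannot occur on that level. If the level is nonetheless what will be analysed, none of the figures above applies.

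**The case against.** **The main analysis is discernible.** A reader might infer that the plan leaves ANOVA, GEE and regression wholly unranked. The word primary is indeed absent from the analysis section, and the sample-size formula would suit a GEE. But the sentence on the initial outcome leads directly into ANOVA and then Scheffe, while the other two methods are given different purposes. This objection stands. What is missing is the visit, the score form and the covariate.

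**Change scores may be intended.** The outcome list points that way, and a change score does use baseline. The sample-size sentence, however, speaks of the mean after intervention, which points to the follow-up value. Neither reading is clearly better supported, and they decide whether the gain is modest or large.

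**Baseline may enter the GEE as a response at time zero.** That would be a legitimate use of it, and the stated purpose of the GEE is compatible with it. The plan does not say so, and the covariate form is partly a matter of preference.

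**The practical weight is limited.** Power is ample, and every gain depends on an assumed r. This also stands. The case rests on narrower intervals and a pre-specified answer at almost no cost.

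**Adjustment is not always more precise.** A reader might infer that it always beats both ANOVAs. The imbalance calculation shows that it need not.

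**Conclusion.** The point holds as a specification gap with a modest, assumption-dependent cost in precision. ANOVA with Scheffe is the natural main comparison, but its visit and score form are open, and none of the three planned methods commits to baseline adjustment.

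For MSC versus control, randomised under both accounts of allocation, adjustment would leave 65% to 95% of the variance of a change-score ANOVA, or 19% to 91% of that of a follow-up-only ANOVA, for r between 0.3 and 0.9. This requires near-balanced baselines, a linear score and equal variances.

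Two stronger conclusions are not supported. The trial is not short of power for its planned difference: at SD 10 it exceeds 99%. Nor would adjustment repair the MNC comparisons. If that group was filled by HLA match, its contrasts are non-randomised, no precision gain over a change score is guaranteed, and adjustment reduces a measured baseline gap only under model assumptions. The documents contradict themselves on whether it was.

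**What to change.** 1. State which score GMFC means. If the classification level is meant, use an ordinal model and revisit the 12-point difference.
2. Make the primary comparison the 12-month score adjusted for its own baseline value. Use ANCOVA, or the planned GEE with group, visit, group-by-visit and baseline terms. A baseline-by-visit term is advisable, though its effect is small.
3. Force baseline into that model rather than leaving it to backward selection, and label the remaining analyses supportive.
4. Scheffe may be kept, applied to the adjusted means.
5. Reconcile the two descriptions of allocation. If MNC was filled by HLA match, label its contrasts non-randomised and state the limits of adjustment.

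The cost is a few lines of plan text and code, and one error degree of freedom in the ANCOVA. No new data are needed.

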CP can result from brain injury occurring during the prenatal, perinatal, or postnatal periods. Seventy to 80 percent of patients with CP have spastic clinical features. In developed countries CP occurs in approximately 2.5/1000 live births.

At present, conventional therapies for children with CP include medications, orthopedic and neurosurgical intervention and neurorehabilitation, but none of these treatments can fundamentally repair damaged neural cells. Stem cells have been investigated as a treatment for neurological damage since the 1990s. There are a number of developmental disorders that are considered targets for stem cell therapy. The most well-known and studied is CP. Stem cell therapy is a new and promising treatment of neurological disorders including CP. For using neurological trial, neurons and glial cells have been generated from Pluripotential stem cells and Multipotential somatic stem cells. There is little clinical trial for stem cell therapy in CP in Iran, that two of them have NCT number. Because of the increasing popularity of postnatal umbilical cord stem cell storage, the most easily accessible current source of stem cells in clinical trials is umbilical cord derived stem cells.

The least invasive source of stem cells, with the fewest ethical issues and with low

processing requirements, is umbilical cord blood (UCB). Safety of allogeneic UCB stem cells confirmed in several clinical trials. UCB is the most easily accessible current source of stem cells in our country. Well-matched allogeneic UCB has been used successfully in children for a number of decades so the risks of using this stem cell source are somewhat understood. There is evidence of in vitro differentiation of UCB into neuronal cells. Umbilical cord-derived mesenchymal stem cells is another source of effective and safe stem cells.

For the first time in our country we planned a trial of stem cells with mesenchymal stromal cells (MSC) derived from umbilical cord (UC), for the treatment of cerebral palsy.

Objectives:

This study designed for the evaluation of safety and therapeutic effects of intrathecal hematopoietic (MNC) and mesenchymal stem cells (MHC) derived from allogeneic umbilical cord in change and probable improvement of developmental functions of spastic CP participants in comparison with control group .

Study design:

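### Low-severity efficiency point: Scheffé is valid but conservative for the two comparisons with control; Dunnett would give tighter intervals, though the power loss at the planned 12-point difference is only 0.3 points

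*Combined protocol and SAP*

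**What the plan says.** The Objectives section sets out to assess the two cell products for change in "developmental functions of spastic CP participants in comparison with control group". The Statistical analysis section takes mean GMFC among the three groups as the initial outcome and begins with an omnibus test: "One-way analysis of variance will be used to investigate the difference between mean GMFC according to the study variables". It continues: "the post-hoc Scheffe test is used to determine the means differences". On the error rate it says only that "All analyses were performed at a significance level of 0.05". It does not list the contrasts to be tested, state sidedness or give a reason for Scheffé.

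The Sample size calculation section plans for "power 80% to achieve 12 score difference in mean of GMFC after intervention", with an SD of 10, and describes the allocation as 108 patients, "which are in each of the three groups MNC, MSC and Control 36 patient allocated". Its formula is for two groups and has no multiplicity adjustment.

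**The concern.** A trial built to compare two active arms with one control has two comparisons that matter. Scheffé protects an unlimited set of contrasts, including weighted combinations that nobody has asked about, and it pays for this with a larger critical value. If only the comparisons with control are of interest, part of the 5% error allowance goes unused. The intervals for the main comparisons are then wider than necessary, and a moderate benefit is somewhat more likely to be missed. Type I error is not inflated, so the stake is precision and power, not validity.

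**Working it through.** **Inputs from the documents.** 36 per arm, SD 10, target difference 12, power 80% and alpha 0.05 (Sample size calculation and Statistical analysis). Error degrees of freedom: 3 × (36 − 1) = 105.

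**Assumptions.** Two-sided tests, no dropout, and a continuous score with SD 10. True differences other than 12 are illustrative and do not appear in the documents.

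**The plan's own figure.** For a single time point the plan's formula gives N = 2(1.960 + 0.842)² / (12/10)² = 15.70 / 1.44 = 10.9, so 11 per group. The repeated-measures factor (1 + (n − 1)ρ)/n cannot exceed 1 for ρ between 0 and 1, so the formula gives at most 10.9 for any number of time points. The section gives no values for n or ρ. The stated 36 per group is therefore not reproduced. This matters below only because it makes 12 points a weak anchor.

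**Critical values at 105 df.**
- Scheffé: √(2 × F(0.95; 2, 105)) = √(2 × 3.083) = 2.483
- Tukey, three pairs: q/√2 = 2.377
- Bonferroni, two comparisons: 2.274
- Dunnett, two comparisons with correlation 0.5, by numerical integration: 2.242
- Single unadjusted contrast: 1.983

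**Familywise error.** Under the global null, the chance that at least one of the two comparisons with control is significant is 2.7% with Scheffé and 5.0% with Dunnett.

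**Interval width.** The standard error of a difference is 10 × √(2/36) = 2.357. Half-widths are 2.483 × 2.357 = 5.85 (Scheffé) and 2.242 × 2.357 = 5.28 (Dunnett). The ratio is 2.483/2.242 = 1.11, whatever the true effect.

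**Power per comparison.** From the noncentral t with noncentrality d/2.357. Losses are taken from unrounded values.

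| True difference | Scheffé | Dunnett | Loss (points) |
|---|---|---|---|
| 5 | 36.3% | 45.5% | 9.2 |
| 5.6 | 46.0% | 55.5% | 9.4 (maximum) |
| 6.7 | 64.1% | 72.5% | 8.5 |
| 8 | 81.7% | 87.4% | 5.7 |
| 12 (planned) | 99.5% | 99.8% | 0.3 |

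The 6.7-point row is roughly where one unadjusted contrast with 36 per arm has 80% power.

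**All three pairs.** Against Tukey, the largest loss is 4.1 points, near a difference of 5.7.

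**ANOVA kept as a gate.** In 200,000 simulated trials at 5.6 points, Dunnett applied only after a significant F test has power 53.2%, against 46.1% for Scheffé. The gain falls from about 9 points to about 7. The gate does not cost Scheffé anything, because a significant Scheffé contrast implies a significant F.

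**The case against.** The strongest reply is that Scheffé is a valid procedure, agrees with the ANOVA before it, and makes almost no difference on the plan's own numbers: 99.5% against 99.8% power at 12 points. That stands. A reader might infer from the 9.4-point maximum that the trial gives up that much power. The documents do not support this, because the maximum arises at less than half the planned difference.

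The reply is weakened, but not removed, by two facts. The interval width does not depend on the effect, and the planned 12 points do not lead to 36 per group. At the 11 per group that the inputs do give, the loss at 12 points would be 9.1 points (59.8% against 68.9%).

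A second reply is that the plan nowhere limits post-hoc testing to control. That also stands. A reader might conclude that Scheffé's wider cover is worth nothing here, but it protects MNC versus MSC and a pooled cells-versus-control contrast, both natural questions in this design. If the three pairs are the target, however, Tukey covers them with a smaller critical value than Scheffé, so Scheffé is still not the efficient choice.

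Third, the scale is uncertain. The Inclusion criteria use GMFC for a classification from 2 to 5, on which a 12-point difference cannot occur. Every power figure here is conditional on a continuous score with SD 10. The figures also concern the single-time ANOVA, not the planned GEE analysis.

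**Conclusion.** The point holds as a cheap, low-severity improvement. For the two comparisons in the objective, Scheffé uses about 2.7% of a 5% familywise allowance and widens simultaneous intervals by about 11%. The power cost ranges from 0.3 points at the planned difference to 9.4 points at worst against Dunnett. It is at most about 4 points against Tukey if all pairs are wanted, and Dunnett's gain near 5.6 points is about 7 if the F test still gates the comparisons. These figures rest on 36 analysed per arm, SD 10, a continuous outcome and two-sided testing.

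The documents do not support calling Scheffé an error. Nor would a sharper test put MNC versus control on a sound footing: Study design and Randomization describe filling the MNC group by HLA match and randomising only the remaining patients between MSC and control. That issue is separate and is not touched by the choice of multiplicity procedure.

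**What to change.** In the Statistical analysis section, name MNC versus control and MSC versus control as the planned contrasts. Replace the Scheffé sentence with two-sided Dunnett comparisons at familywise 0.05, reported with simultaneous 95% confidence intervals. State that these comparisons do not depend on the omnibus F test; otherwise part of the gain is lost. Report MNC versus MSC as secondary. If all three pairs are of equal interest, say so and use Tukey instead. Bonferroni for two comparisons (critical value 2.274) is a simple alternative that recovers most of Dunnett's gain.

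The cost is a few sentences and no extra patients or data. The downside under Dunnett is that MNC versus MSC and any pooled contrast fall outside the protected family, and the text should say this.
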